- 2. Manual therapy techniques commonly used in clinical practice to manage symptoms, e.g. used to lengthen tight muscles or reduce active trigger point pain presentations.

3.3. physiological effect:

Improper control is characterized by changes in muscle activation levels. More specifically, lower activity of the serratus anterior, higher activity of the upper and lower trapezius, and lack of coordination between the different parts of the trapezius have been observed. This inadequate muscle control is believed to contribute to a reduction of amplitude in posterior tilting and lateral rotation of the scapula during arm elevation. Lower activity of the infraspinatus and subscapularis as well as inadequate coactivation of the scapulohumeral muscles have also been reported. This abnormal muscle control is most likely associated with a reduction of the subacromial space leading to impingement (Hawkes et al., 2019).

Motor control include production of reflexive, automatic, adaptive and voluntary movements and the performance of efficient, coordinated, goal-directed movement patterns which involves multiple body systems (input, output, and central processing). Evidence suggests exercise program mainly focusing on motor control principle for the scapulothoracic joint has been a promising treatment option for shoulder impingement (Hara, 2020).

CHAPTER III

SUBJECTS, MATERIALS AND METHODS

In this part of the study, the materials and methods will be presented under the following headings: subjects, equipment, procedures of the study and the statistical procedures.

1-Subjects:

1.1.Sample size:

Sample size calculation was done using, shoulder function as reported in (Mohite and Kanase, 2014), with 90% power at $\alpha = 0.05$ level, number of measurements 2, for 2 groups and effect size = 0.45 using F-test MANOVA repeated measures within and between interaction. The minimum proper sample size is 54 subjects, adding 6 (11%) subjects as drop out, so total sample size is 60 subjects 30 in each group. The sample size was calculated using the G*Power software (version 3.0.10) (figure 2).

[figure not shown]

Figure (2): sample size calculation

sixty patients suffering from post-mastectomy shoulder dysfunction will participate in this study. Their ages will range from 40 to 55 years. The participants will be selected from Cairo university hospitals.

1.2. Design of the study:

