In this randomised controlled trial study (RCT), the patients will be randomly assigned into two equal groups (30 patients for each group):

1.2.a. Group A (study group):

This group will include 30 patients with post mastectomy shoulder dysfunction who will receive motor control retraining exercises in addition to their conventional physical therapy program, three sessions per week for 8 weeks, for 45:60 minutes according to patient's ability (**Bae et al.,2011**).

1.2.b. Group B (control group):

This group will include 30 patients with post mastectomy shoulder dysfunction who will receive conventional physical therapy program in the form of shoulder joint mobilization, posterior capsule stretching and shoulder range of motion exercise (ROM) (Codman's pendulum exercises) for 30 minutes according to patient's ability, three sessions per week for 8 weeks (**Duzgun et al.**, 2019; Yiasemides et al., 2011).

1.3. Criteria for the patient selection:

1.3.a -Inclusion Criteria:

The subject selection will be according to the following criteria:

- Female patients with age range between 40-55 years.
- All patients have shoulder dysfunction.
- Patients were 2 months to 4 months post modified radical mastectomy or axillary lymph node dissection.
- Patients received their radiotherapy or chemotherapy or both.

1.3.b- Exclusion Criteria:

The potential participants will be excluded if they meet one of the following criteria:

- Rheumatoid arthritis.
- History of trauma or accidental injuries.
- Neurological involvement (stroke, Parkinsonism).
- History of surgery on involved shoulder.
- Diabetic patient.
- Moderate and severe lymphoedema.

2-Tools and equipment:

2.1. Measurement tools and equipment:

All Measurements will be taken before the treatment (pre-treatment) and after 8 weeks (post-treatment).

2.1.a- Shoulder Pain and Disability Index (SPADI):

The SPADI is a self-administered questionnaire that contains thirteen items which assess two domains (pain and disability) (Shamley et al., 2012). It has an 8-item subscale to evaluate disability and a 5-item subscale to measure pain. Each subscale is summed and transformed to a score out of 100. A mean is taken of the two subscales to give a total score out of 100, higher score indicating greater impairment or disability (Breckenridge and McAuley, 2011). The Arabic version of SPADI has excellent validity and reliability (Alsanawi et al., 2015)

2.1.b- Instrumented digital hand-held dynamometer:

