Hand-held dynamometry (Lafayette manual muscle tester) will be used to measure isometric strength of shoulder flexion and abduction. It is an ergonomic hand-held device for objectively providing reliable, accurate readings that conform to most manual muscle testing protocols. It has good to excellent validity and reliability for most measures of isometric muscle strength particularly for proximal muscle groups. It has a large, easy-to-read LCD screen that displays results in both pounds and kilograms. It also has a weight capacity of up to 300 lbs. (mentiplay et al., 2015). Fig. (3).

Fig. (3) Lafayette hand-held dynamometer

2.1.c- Digital inclinometer:

A digital inclinometer is used to measure shoulder flexion, abduction and upward rotation of scapula. It has digital screen that display the angle at which the inclinometer is situated allowing direct joint angle measurements (An et al., 2021).

2.2. Therapeutic Equipment and Tools:

Motor control retraining exercises for scapular muscles.

3-Procedures of the study:

3.1. Measurement procedures:

3.1.a. The Shoulder Pain and Disability Index (SPADI):

To answer the questions, the patient is instructed to place a mark on the 100mm straight line, this line represents a continuum between "no pain" (zero) and "the worst pain that the patient could feel" (ten) for pain dimension and "no difficulty" (zero) and "so difficult it requires help" (ten) for the disability dimension, respectively. To calculate a final percentage score for assessing shoulder

dysfunction, a mean is taken of the two subscales to give a total score out of 100, higher score indicating greater impairment or disability (**Brindisino et al., 2021**). The Arabic version of SPADI has excellent validity and reliability (**Alsanawi et al., 2015**)

3.1.b- Instrumented digital hand-held dynamometer:

A handheld dynamometer will be used to assess maximal strength pre-treatment and post treatment. Maximal strength tests for shoulder flexion and abduction will be measured. When applying the manual resistance for each test the handheld dynamometer is used to obtain force measures. Two trials were performed for each shoulder motion (Scibek and Carcia, 2012).

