traction and oscillating movements and provide early motion of joint structures and synovial fluid. No weight will be used initially. When the patient will tolerate stretching, a weight will be added to the hand or as wrist cuffs to cause further distraction force. To direct the stretch force to glenohumeral joint, stabilize the scapula against the thorax manually or with a belt (Patel, 2022).

4.Statistical procedures:

The collected data will be statistically analysed using:

- Descriptive statistics (mean and standard deviations).
- Inferential statistics: unpaired t-test will be used to compare subjects' characteristics of the two groups.
- Repeated measures MANOVA will be used to compare all dependent variables within and between groups.
- Statistical analysis will be conducted using SPSS for Windows, version 20 (SPSS, Inc., Chicago, IL). Statistical significance will be set at the (p< 0.05).

References

Alsanawi, H. A., Alghadir, A., Anwer, S., Roach, K. E., and Alawaji, A. (2015). Cross-cultural adaptation and psychometric properties of an Arabic version of the Shoulder Pain and Disability Index. *International journal of rehabilitation research*. *Internationale Zeitschrift fur Rehabilitationsforschung*. *Revue internationale de recherches de readaptation*, 38(3): 270–275.

An, D. I., Park, J. E., Lee, C. H., & Kim, S. Y. (2021). Reliability of scapular upward rotation and anterior-posterior tilt measurements using a modified digital inclinometer in patients with subacromial impingement syndrome. *Journal of Back and Musculoskeletal Rehabilitation*, 34(5), 837-843.

Bae, Y. H., Lee, G. C., Shin, W. S., Kim, T. H., & Lee, S. M. (2011). Effect of motor control and strengthening exercises on pain, function, strength and the range of motion of patients with shoulder impingement syndrome. Journal of Physical Therapy Science, 23(4), 687-692.

Bakhsh W., and Nicandri G. (2018): "Anatomy and physical examination of the shoulder". Sports medicine and arthroscopy review; 26(3): e10-e22.

Borstad J. D., and Szucs K. A. (2012): "Three-dimensional scapula kinematics and shoulder function examined before and after surgical treatment for breast cancer". Human movement science; 31(2): 408-418.

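### With one pre-treatment and one 8-week value per outcome, the powered group-by-time interaction is, outcome by outcome, a change-score test: valid and correctly sized, but generally less precise than ANCOVA on the baseline already collected

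*Protocol*

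**What the plan says.** Three places in the protocol fix the analysis.

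- **Section 2.1 (measurement tools and equipment):** "All Measurements will be taken before the treatment (pre-treatment) and after 8 weeks (post-treatment". Each outcome therefore has exactly two values per woman.
- **Section 1.1 (sample size):** the calculation uses "number of measurements 2, for 2 groups and effect size = 0.45" and the "F-test MANOVA repeated measures within and between interaction", with 90% power at alpha 0.05. The result is: "The minimum proper sample size is 54 subjects, adding 6 (11%) subjects as drop out", giving 60, or 30 per group.
- **Section 4 (statistical procedures):** "Repeated measures MANOVA will be used to compare all dependent variables within and between groups". This is the only method named for the outcomes. The pre-treatment value enters as one of the repeated responses, and no baseline covariate is mentioned.

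**The concern.** With two groups and two time points, the interaction for one outcome asks whether the mean change differs between groups. That amounts to subtracting the whole baseline value from the 8-week value. ANCOVA subtracts only the share of baseline that the data support. Under randomisation both approaches estimate the same treatment effect, but the change score usually does so with more noise.

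What is at stake is efficiency: generally wider confidence intervals and lower power than the same 60 women could give, by an amount that depends on a correlation the protocol does not report. Because the protocol itself names the method, this is a choice it has made and not a detail it has left open.

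**Working it through.** **Inputs from the protocol.** Two groups, two measurements, effect size f = 0.45, alpha 0.05, power 90%, N = 54 (60 with drop-out), 1:1 randomisation.

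**Assumed, because the protocol gives neither.** The pre-post correlation rho, and k = post SD / pre SD. Both are shown as ranges.

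**Step 1: reproduce 54.** For the interaction, take a noncentral F with 1 and N − 2 degrees of freedom and lambda = N × 0.45² = N × 0.2025.

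| N | lambda | power |
|---|---|---|
| 52 | 10.530 | 0.889 |
| 53 | 10.732 | 0.895 |
| 54 | 10.935 | 0.901 |
| 60 | 12.150 | 0.929 |

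The smallest N reaching 90% is 54, as stated. With equal groups, f = 0.45 corresponds to 2 × 0.45 = 0.90 SDs of the change score.

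**Step 2: the interaction is the change-score test.** On a simulated data set the interaction F and the squared t on change scores were both 0.25509. In simulations of 27 per arm with no effect (20,000 runs each; rho 0.3, 0.5, 0.7), the change-score test rejected in 4.7%, 4.9% and 5.2% of runs, so it holds its level.

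**Step 3: compare variances.** In units of the pre-treatment variance:

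- change score: 1 + k² − 2·rho·k
- ANCOVA: k²(1 − rho²)
- difference: (1 − rho·k)², which is never negative and is zero only when rho·k = 1

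The variance ratio, ANCOVA over change score, is k²(1 − rho²)/(1 + k² − 2·rho·k). At k = 1 it is (1 + rho)/2.

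**Step 4: ANCOVA power for the same effect.** Use lambda = N × 0.2025 / [ratio × (1 + 1/(N − 4))] with 1 and N − 3 degrees of freedom. The factor 1 + 1/(N − 4) is the cost of estimating the slope. Example at rho 0.5, k = 1, N = 54: 10.935 / (0.75 × 1.02) = 14.294, giving power 0.960.

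Equal SDs (k = 1):

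| rho | ratio | power, N=54 | power, N=60 | even N for 90% | CI width relative to change score, N=54 |
|---|---|---|---|---|---|
| 0.3 | 0.65 | 0.979 | 0.988 | 38 | 0.815 |
| 0.5 | 0.75 | 0.960 | 0.975 | 44 | 0.875 |
| 0.7 | 0.85 | 0.936 | 0.958 | 48 | 0.932 |
| 0.8 | 0.90 | 0.923 | 0.947 | 50 | 0.959 |
| 0.9 | 0.95 | 0.909 | 0.936 | 54 | 0.985 |
| interaction test | 1 | 0.901 | 0.929 | 54 | 1 |

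At rho 0.96 the ANCOVA power at N=54 is 0.9005, so the gain has gone.

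Unequal SDs at rho 0.7:

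| k | ratio | power, N=54 | even N for 90% |
|---|---|---|---|
| 0.8 | 0.628 | 0.982 | 36 |
| 0.9 | 0.751 | 0.960 | 44 |
| 1.1 | 0.921 | 0.917 | 52 |
| 1.2 | 0.966 | 0.905 | 54 |
| 1.43 | 1.000 | 0.895 | 56 |

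The last row is the worst case (0.7 × 1.43 ≈ 1): 0.895 against 0.901, a loss of about 0.6 points.

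**Step 5: simulation check** (20,000 runs per row, N = 54). Change-score power was 0.896 to 0.904 throughout. ANCOVA at k = 1 gave 0.979, 0.960, 0.938, 0.922 and 0.906 for the five correlations, and 0.895 at rho 0.7, k = 1.43. These agree with the formulas.

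**The case against.** **The plan is not in error.** This stands. The test is valid, 54 is right for it, and 60 women give about 93% single-outcome power. A reader might infer that the trial is underpowered or its analysis biased; the figures show neither.

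**The size of the gain is unknown.** This also stands. At N=60 with equal SDs the gain is about 6 points at rho 0.3, 3 at rho 0.7 and under 1 at rho 0.9, and it can vanish. But the outcomes are asymmetric: the worst case costs about 0.6 points at N=54, while plausible cases gain several.

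**Section 4 may mean one joint test of all outcomes.** It can be read that way. The single-outcome reading comes from section 1.1, which sizes the interaction on one quantity. A reader might carry the power figures over to a joint MANOVA; they do not apply there, and the loss against such a test has not been worked out.

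**Baseline adjustment could sit in a separate analysis plan.** It could, but the protocol names a different method, so the two would then have to be reconciled.

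**Does the change require choosing a lead outcome?** A reader might think so, and might take it to be SPADI. Section 1.1 names only shoulder function, and the scoring text in section 3.1.a suggests SPADI without establishing it. Ordering the outcomes is a separate matter, and adjusting for baseline does not depend on it.

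**Conclusion.** The point holds as an inexpensive improvement in efficiency. It is not a correction of an invalid analysis. For each single outcome, the method fixed in section 4 and powered in section 1.1 makes a generally less precise use of a baseline that is collected anyway.

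The direction rests on randomisation and the variance identity in step 3. The size rests on the assumed rho and SD ratio, and on holding the planned effect at 0.90 change-score SDs. For example, at rho 0.5 with equal SDs and N=54, the chance of missing the planned effect falls from about 10% to 4%, and the 95% CI is about 12% narrower. The sample size is adequate and need not change.

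**What to change.** **Section 4.** Replace the sentence on repeated measures MANOVA with:

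> For each outcome, the between-group comparison at 8 weeks will be by ANCOVA with group as factor and the pre-treatment value of the same outcome as covariate, reporting the adjusted mean difference with 95% CI; within-group changes will be reported descriptively.

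**Section 1.1.** Add a note that 54 (60 with drop-out) was computed for the group-by-time interaction and is in general conservative for ANCOVA.

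**Cost.** Two short edits, with no new data, visits or patients. ANCOVA uses one degree of freedom per outcome and loses at most about 0.6 points of power at N=54. Two features of the current plan change. Per-outcome between-group tests replace any joint test, and the within-group comparison becomes descriptive.
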